## **Primary Objective 2**

We approximate a sample size needed for Bland-Altman plots. We calculate the minimum sample size needed to detect a difference. A prior study found the following measurements:

	Mean [SD] (mcmol/L)
Colour 1	106 [43]
Colour 2	108 [38]
Colour 3	113 [38]
Colour 4	145 [34]

From this, we take a mean difference of 10 to be our estimated effect size. From above, we take the two largest standard deviations for a cautious estimate of the standard dedication of difference (SD= $\sqrt{43^2+38^2}=57.4$ ). We set our targeted clinical agreement limit at 145 mcmol/L. Under these assumptions, a sample size of 80% requires 140 study participants , which from above we should easily exceed.

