Following initial sample size calculations (detailed in Section 10) it has been estimated that a total of 560 participants will need to be recruited, to adequately power the study's Primary Objectives 1 and 2. Therefore, we will aim to recruit a

minimum of 28 participants at each site. An initial recruitment window will aim to recruit 10 participants per site. If there is insufficient recruitment to particular skin tone groups, recruitment windows can be reopened in centres where recruitment of participants of that group is most likely.

Data collection periods may need to be staggered according to the timings of individual Trust R&D approval processes. The total anticipated time for the study is currently 18 months, of which approximately the first 9 months will include local site approval processes and data collection, followed by a 9 month period of analysis and preparation for dissemination (see Gantt chart attached for further detail).

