Primary objective 1 will be using a linear mixed model, with skin tone and confounders as fixed effects and hospital as a random effect. The outcomes will be the coefficient difference between baseline skin tone and the other 3, with 95% CI.

Primary objective 2 will use the Bland-Altman to detect differences of measurement between skin tones, stratified by method of how the measurement for how serum bilirubin was taken. The mean of the differences will be provided with 95% CI, along with the IQR of difference with accompanying p-value. The rate of over/under-estimation will also be estimated between different skin tones. Bland-Altman plots will be reported as well as Specificity and sensitivity analyses using Receiver operating characteristic (ROC) curves.

Secondary Objective 1: Primary length of admission differences between skin tone will be compared using survival analysis of time to event data (Kaplan-Meier plot, Cox Proportional Hazards Model). The need for interventions including phototherapy and exchange transfusion will be done using generalised linear mixed models, with outcomes reported as Odds Ratios with 95% CI.

Age of infant at measurement is an important metric and shall be included as a fixed covariate in all models other than Bland-Altman (baseline model). Additionally, IMD and gestational age may be included as additional covariates (adjusted model). However, due to the complex relationship between skin colour and medical intervention, we run the risk of over-adjusting on covariates and inducing collider bias and/or mediators. For example, skin tone may affect what the indication for jaundice assessment was, and this in turn may affect the outcome of bilirubin and if there was a delay for treatment, making it a mediator. With sufficient time, this relationship may be explored to see if different skin tones are affected by how their jaundice is first indicated, which influences clinical guidelines if an association is found between skin tone and indication which in turn affects bilirubin levels.

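### The sample size of 140 for Primary Objective 2 appears to be a one-sample limits-of-agreement figure, so the claim of adequate power is unsupported for the planned comparison between skin tones

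*Protocol*

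**What the plan says.** Section 10.1, Primary Objective 2, opens with "We approximate a sample size needed for Bland-Altman plots" and cites a method paper on sample size for agreement between two methods of measurement. It then gives the purpose as "We calculate the minimum sample size needed to detect a difference". The inputs are:

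- A mean difference: "we take a mean difference of 10 to be our estimated effect size".
- An SD of the difference of 57.4, the root of 43² + 38², justified as "we take the two largest standard deviations for a cautious estimate of the standard dedication of difference". The 43 and 38 are the SDs of two colour groups in a prior study's table.
- An agreement limit: "We set our targeted clinical agreement limit at 145 mcmol/L".

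At 80% (printed as a sample size, evidently meaning power) the result is 140 participants, which the section expects to exceed comfortably. Section 8 states that "it has been estimated that a total of 560 participants will need to be recruited, to adequately power the study's Primary Objectives 1 and 2".

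The analysis is fixed in Section 10.2: "Primary objective 2 will use the Bland-Altman to detect differences of measurement between skin tones", stratified by how serum bilirubin was measured. The same section has the sample sizes for both primary objectives recalculated on interim data until both targets are met.

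**The concern.** The sample size and the analysis address different questions. An agreement limit has no role in a test of means. It belongs to a calculation that asks whether, in one undivided set of paired differences, both limits of agreement can be shown to lie inside ±145. The planned analysis asks whether the TcB-SBR difference varies from one skin tone to another. No tone group size and no between-tone contrast enters the 140.

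At stake is what the 80% and the adequacy statement mean. A reader of the results would take them as applying to the tone comparison, which is central to a study of inequity in jaundice assessment. The recalculated Objective 2 target can also shorten or lengthen recruitment, so it matters which question that target serves.

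**Working it through.** **1. Reproducing the 140.** Inputs from Section 10.1: mean difference 10, SD = √(43² + 38²) = 57.4, limit 145, power 80%. Alpha is not stated for this objective; two-sided 0.05 is assumed from the 95% CI in Section 10.2. One-sample limits-of-agreement power requires both confidence bounds of mean ± 1.96 SD to fall inside ±145:

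- SE = SD × √(1/n + 1.96²/(2(n − 1))). At n = 140 this is 57.4 × √(1/140 + 1.96²/278) = 8.31.
- Non-centrality for the upper limit: (145 − 10 − 1.96 × 57.4)/8.31 = 2.71. For the lower limit: (145 + 10 − 1.96 × 57.4)/8.31 = 5.11.
- Power from the non-central t distribution: 77% at n = 140. For 80%, n = 152 (two-sided 0.05) or n = 120 (one-sided 0.05).

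The 140 is therefore not reproduced exactly. Small changes of one input come close: SD 57 gives 141, mean difference 9 gives 140, limit 146 gives 140. Formulas for means with SD 57.4 are far away: a one-sample test of a mean difference of 10 needs 259, and a two-sample test needs 518 per group.

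**2. Direction of the 10.** Same formula, n = 140, SD 57.4, limit 145, two-sided 0.05:

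| Mean difference | Power |
|---|---|
| 0 | 95% |
| 10 | 77% |
| 20 | 32% |

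Power falls as the difference grows. In this formula the 10 is a bias that makes agreement harder to declare, not an effect to be detected.

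**3. Between-tone contrast, as illustration only.** Assumptions, none of which the protocol fixes for Objective 2:

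- 10 is the between-tone difference in mean TcB − SBR.
- The 50/20/20/10 tone mix is borrowed from Objective 1, giving 280/112/112/56 of 560.
- Tone 1 is the reference.
- All 560 infants have both readings.
- Alpha is two-sided 0.05, without adjustment for multiple contrasts.

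SE = √(SD₁²/n₁ + SD₂²/n₂); power = Φ(10/SE − 1.96).

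| SD used | Tone 2 or 3 vs 1 (280 vs 112) | Tone 4 vs 1 (280 vs 56) |
|---|---|---|
| 57.4 in each group | SE 6.42, 34% | SE 8.40, 22% |
| Table SDs (43; 38; 34) | SE 4.42, 62% | SE 5.22, 48% |
| 40 (assumed) | 61% | 40% |
| 30 (assumed) | 85% | 62% |
| 20 (assumed) | 99% | 93% |

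**4. SD at which 560 pairs would suffice.** 80% power for a difference of 10 needs SD ≤ 10/[(1.96 + 0.84) × √(1/n₁ + 1/n₂)]. With √(1/280 + 1/112) = 0.1118 the bound is about 32. With √(1/280 + 1/56) = 0.1464 it is about 24.

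**5. Number of pairs.** SBR is taken only in routine care (Section 9, Laboratory assessments), so 560 pairs is an upper bound. If half the infants had both readings (280 pairs), power at SDs of 20, 30 and 40 would be 89/56/35% for tone 2 or 3 vs 1 and 68/36/23% for tone 4 vs 1. Stratifying by SBR method divides the pairs further.

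**The case against.** Four points can be made for the protocol.

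- **The attribution is inferred.** The stated inputs give 152 or 120, not 140. This stands, and the origin of the figure can only be called likely. It rests on the cited method, the agreement limit and the near-recovery with slightly different inputs. The mismatch does not depend on the attribution, since no tone group appears in the calculation however it was run.
- **The objective is also worded as agreement.** The synopsis and Section 5.2 speak of agreement between TcB and SBR, for which an agreement sample size is relevant. That is fair, and the calculation need not be discarded. It does not cover the between-tone analysis that Section 10.2 specifies.
- **Interim recalculation may repair this.** Section 10.2 uses bilirubin measures and skin tone in the updates, and Section 8 allows windows to reopen for under-recruited tones. Both help, but no between-tone calculation is named. It would be equally speculative to assert that the agreement formula will be reapplied.
- **Results come with 95% CIs.** Intervals for the mean differences would show imprecision, and nothing in the protocol says a null result will be read as equal performance.

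A reader might infer that the study has only 22–34% power on its own inputs. The documents do not support that. The 57.4 combines the SDs of two colour groups and is not an SD of within-infant TcB-SBR differences. The 10 is not defined as a between-tone contrast, and the tone mix and reference tone come from Objective 1. With other SDs the same calculation gives anything up to 99% and 93%.

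**Conclusion.** The point holds as a mismatch between sample size and analysis, not as an arithmetic error. The 140 appears to concern limits of agreement in one pooled sample. It does not power detection of a difference, and the statements that 560 is adequate and 140 easily exceeded are unsupported for the between-tone comparison.

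Whether the study is in fact underpowered cannot be determined from the protocol. Under the assumptions listed in the working, 560 complete pairs would give 80% power for a difference of 10 only if the SD of paired differences is at most about 32 (tone 2 or 3 vs 1) or 24 (tone 4 vs 1). The protocol gives no such SD and no expected number of pairs per tone. This should be fixed, but it does not undermine the design.

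**What to change.** 1. In Section 10.1, Primary Objective 2, relabel the 140 as a sample size for the limits of agreement in one pooled sample. State alpha and sidedness, and correct the figure to what the stated inputs give (152 two-sided, 120 one-sided).
2. Remove the statements that it serves to detect a difference and that it will easily be exceeded, as far as they refer to tone differences.
3. Add power or detectable difference for the between-tone contrast of Section 10.2 at the planned size. Use a justified SD of paired TcB-SBR differences, or a stated range updated from the interim data, and the expected number of infants per tone with both readings. The 34% and 22% should not be printed as the study's power, because they rest on an SD that is not a paired one.
4. Restate the adequacy claim in Section 8 to match.
5. Name the between-tone calculation as the one used in the Section 10.2 updates for this objective.

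The cost is protocol wording and a short calculation. No increase in enrolment is required. The stated power may become less favourable, depending on the paired SD.

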#### **Laboratory assessments:**

No additional laboratory assessments will be carried out on participating neonates by the research team. SBR measurements will only be done by the normal clinical team as part of routine clinical care.

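### The Primary Objective 2 sample size is not a valid Bland-Altman calculation for TcB-SBR agreement, so the claim that 560 infants adequately power that objective is unsupported

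*Protocol*

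**What the plan says.** Protocol section 10.1, Primary Objective 2, states its purpose as "We approximate a sample size needed for Bland-Altman plots". It tabulates one mean [SD] per colour group from a prior study: 106 [43], 108 [38], 113 [38] and 145 [34] mcmol/L. It then builds three inputs.

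- Mean difference: "we take a mean difference of 10 to be our estimated effect size".
- SD of the difference: "we take the two largest standard deviations for a cautious estimate of the standard dedication of difference", computed as √(43² + 38²) = 57.4.
- Agreement limit: "We set our targeted clinical agreement limit at 145 mcmol/L".

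The result is that "a sample size of 80% requires 140 study participants" (80% is presumably the power), followed by the remark "which from above we should easily exceed". Section 8 says 560 participants adequately power both primary objectives.

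Two other places bear on this. Section 10.2 says "Primary objective 2 will use the Bland-Altman to detect differences of measurement between skin tones, stratified by method" of serum measurement. Section 9, Laboratory assessments, says "SBR measurements will only be done by the normal clinical team as part of routine clinical care".

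**The concern.** Bland-Altman planning rests on the mean and SD of the difference between two methods in the same subject. Here that is TcB minus SBR within an infant. The root-sum-of-squares of two SDs is the SD of a difference between two independent quantities. Section 10.1 applies it to two colour groups, so the result describes the gap between unrelated infants, not disagreement between two devices.

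The agreement limit should be the largest TcB-SBR discrepancy that clinicians would tolerate. A value of 145 is larger than the whole mean level in Colours 1 to 3, so as a planning target it places almost no demand on precision.

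Finally, the 140 is compared with all infants enrolled. The quantity that matters is the number of TcB-SBR pairs in each tone.

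At stake is the only sample-size justification for one of two primary objectives, and the precision that can be promised for the darkest tone group, which is central to the study's question.

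**Working it through.** **Inputs.** From section 10.1: difference 10, SDs 43 and 38, limit 145, n = 140, tone shares 50/20/20/10%. From section 8: total 560. No alpha is stated for this calculation, so two-sided 0.05 is assumed, with one-sided 0.05 as the alternative.

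**1. The SD.** √(43² + 38²) = √(1849 + 1444) = √3293 = 57.38. The arithmetic is right. The 43 is from Colour 1 and the 38 from Colour 2 or 3, so the formula joins two groups of infants and takes zero correlation. The table does not name what was measured, but means of 106 to 145 beside a separately chosen difference of 10 make sense only as bilirubin levels. Purely as illustration, had 43 and 38 been the TcB and SBR SDs in the same infants, √(43² + 38² − 2ρ·43·38) would be 40.7, 26.0 and 18.8 for assumed ρ of 0.5, 0.8 and 0.9.

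**2. The difference of 10.** The gaps between the tabulated means are 2, 5, 7, 32, 37 and 39. None is 10, and none is a TcB-SBR difference.

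**3. The limit of 145.** It equals the Colour 4 mean and exceeds 106, 108 and 113. That it was taken from the table is an inference; no other reason is given.

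**4. Reproducing 140 from the stated inputs.**
- Limits of agreement: 10 ± 1.96 × 57.38 = −102.5 to 122.5.
- SE of a limit at n = 140: 57.38 × √(1/140 + 1.96²/(2 × 139)) = 8.31.
- Standardised margins: (145 − 122.47)/8.31 = 2.71 (upper) and (145 − 102.47)/8.31 = 5.12 (lower).
- Two-sided 0.05: power is 76.7% by non-central t and 75.8% by simulation. About 152 to 156 infants give 80%.
- One-sided 0.05: power is about 84 to 85%, and about 118 to 123 infants suffice.
- SD 57, or difference 9, or limit 146, changed one at a time, gives 140 or 141 (two-sided).

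So 140 is reproduced only approximately, and the gap is small.

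**5. What 140 is compared with.** 560 × 0.50/0.20/0.20/0.10 = 280/112/112/56. Only tone 1 exceeds 140. These are infants enrolled. Pairs will be fewer, because SBR is taken only in routine care and section 7 describes SBR as following a TcB within a threshold of the treatment line. Section 10.1 makes no allowance for missing data, and section 10.2 splits further by SBR method. No pair rate is given.

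**6. Direction of the net error.** An SD that is too large inflates n; a limit that is too wide deflates it. With a difference of 10, two-sided 0.05 and assumed paired inputs, the required n is:

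| Assumed SD | Assumed limit | n for 80% power |
|---|---|---|
| 25 | 80 | 36 |
| 20 | 60 | 82 |
| 30 | 80 | 168 |
| 20 to 30 | 145 (kept) | 7 or fewer |

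The requirement may lie above or below 140, and above or below the 56 expected in tone 4.

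**7. Precision whatever the SD.** The 95% CI half-width is 1.96/√n SDs for the bias and 1.96 × √(1/n + 1.96²/(2(n − 1))) SDs for a limit of agreement. If every infant had a pair:

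| Pairs | Bias | Limit of agreement |
|---|---|---|
| 280 | ±0.12 SD | ±0.20 SD |
| 112 | ±0.19 SD | ±0.32 SD |
| 56 | ±0.26 SD | ±0.45 SD |

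Tone 4 is about 2.2 times less precise than tone 1.

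**The case against.** The best defence is that the plan corrects itself. Section 10.2 redoes the sample size on accumulating bilirubin, skin tone and age data until both primary objectives are met, and may extend the study. Section 8 lets recruitment windows reopen for an under-recruited tone. The tone split is a census-ethnicity proxy used for simulation, not an allocation, so 56 in tone 4 is not fixed. This stands in part: recalculation could replace the SD, and reopening could raise tone numbers. But neither provision revisits the 145, sets a target per tone or counts pairs. Recalculation could even mislead: a realistic paired SD with 145 retained could cut the requirement to single figures, and section 10.2 allows the study to be shortened.

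A reader might infer three stronger things, none of which the document supports.

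- That tone 4 is underpowered. Per-tone power computed from 57.4 and 145 would look poor, but it rests on the very inputs that are invalid. Step 6 shows that 56 pairs could be enough or too few.
- That TcB would be declared accurate whenever it stays within ±145. Section 10.2 contains no test against that limit. It reports the mean difference with CI, the IQR of differences, over- and under-estimation rates, plots and ROC curves. The 145 is only a planning value.
- That 140 is a plain arithmetic error. Alpha is unstated, the calculation is called approximate, and a one-sided alpha more than covers 80%.

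**Conclusion.** The calculation does not support the sample size for Primary Objective 2. The SD is of the wrong quantity, the difference of 10 is not derivable from the table it is attributed to, the limit is unexplained and larger than most of the mean levels, and the pooled 140 is compared with enrolment when the analysis needs pairs by tone. At the assumed split only tone 1 (280) exceeds 140, before any loss of pairs.

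The adequacy claim in section 8 is therefore unsupported, not shown to be false. The true requirement cannot be derived from the protocol, because it gives no SD of TcB-SBR differences. The conclusion rests on reading the tabulated values as bilirubin levels, which is an inference. The shortfall of 140 against 152 to 156 depends on an assumed two-sided alpha and is secondary.

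**What to change.** Replace the Primary Objective 2 paragraph in section 10.1.

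- Use the SD of paired TcB-SBR differences, from a paired source or from the first recruitment window.
- Have the study clinicians set and justify an agreement limit on the difference scale.
- State alpha and its sidedness.
- Express the target as TcB-SBR pairs in each skin tone, use that target in the section 10.2 recalculation and report pair counts by tone.
- Delete the remark that 140 will easily be exceeded. Instead give the expected pairs per tone at 560, with the assumed pair rate, and the CI half-widths of the bias and limits of agreement.
- Amend section 8 so that it claims no more than the new calculation supports.

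The cost is a rewritten paragraph, one extra count in recruitment reports and a less favourable stated precision for tone 4. Restating this needs no extra patients. It is best done before the first recalculation, so that 145 is not carried into it.

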# 7. Study population

The annual number of deliveries per NHS Trust in England ranged from 3,000 to 13,000 in the year 2022 to 20239. NICE guidance recommends that all newborn babies are examined for jaundice at every opportunity, especially in the first 72 hours5. If jaundice is suspected, a bilirubin level should be measured. This is primarily done by midwives either in the community or in a secondary care setting. While exact guidelines vary within secondary care settings, TcB is commonly used in neonates over 24 hours of age who visibly appear jaundiced or meet a risk factor for jaundice1. TcB measurements within a certain threshold of the phototherapy treatment line should then undergo SBR testing5. As jaundice affects approximately

60% of term newborn babies, sufficient numbers of patients are expected to meet study inclusion criteria during a short timeframe.

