## **Screening and recruitment:**

- On data collection days, staff members carrying out jaundice assessments in relevant inpatient areas will be notified and asked to alert the research team when any neonates are undergoing their first TCB or SBR
- Standard clinical care will not be delayed for enrollment
- Identification of potential eligible babies will occur via a written identification table in postnatal areas. Outcomes, i.e. included or excluded, and reasons for exclusion will be noted in the infant's clinical record.
- The research team at each site will consist of the local lead and a number of additional data collectors who have undergone training. These individuals will review whether or not these neonates meet the eligibility criteria, and approach the birthing parent to discuss the study if eligible
- Study data will be collected in participants where all eligibility criteria are met

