#### **Primary Objective 1**

We will be using a linear mixed effects model, where the confounders will be adjusted for as fixed effects, and hospitals will be fitted as a random effect. Due to the complexity of the model we will be using, the optimal method of calculating the sample size requirement *a priori* is with simulation, using *simr* in R^12. We use the following simulated dataset:

[figure not shown]
- Exposure Our exposure, skin tone, will be on 4 levels, with 1 being the lightest and 4 the darkest. No recent research on skin tone within London has been found, therefore we refer to the latest UK census results for ethnicity. For a conservative estimate, we will simulate the data for ethnicity that we would expect in London to act as a proxy for skin tone, as with the 6 categories of ethnicity (White (53.8%), Black (13.5%), Asian (20.7%), Mixed (5.7%) and Other (6.3%)). Therefore we simulate data with probability 50%, 20%, 20% and 10% for tones 1,2,3 and 4, respectively.
- We assume that we will have 20 hospitals collecting data, therefore we have 20 clusters to be a random effect
- The outcome will be simulated depending on skin tone and age. Age will be uniformly distributed between ages 0 and 96 hours. Bilirubin mean will be simulated according to the following formula:
  - Bilirubin (μmol/L)=2.6\*age (hours)+60+20\*skin tone+60 with standard deviation 10. The coefficient and intercept, 2.6 and 60 respectively, is to fit the line where babies begin to need phototherapy according to the NICE jaundice treatment threshold graphs.

We wish to achieve an effect size of 10 µmol/L for skintone 2 compared to skin tone 1, 20 µmol/L for skin tone 3 compared to skin tone 1, and 30 µmol/L for skintone 4

compared to 1. We perform 100 simulations for each simulated cluster size (between cluster sizes of 10 and 50 neonates), and estimate the average power achieved. Assuming a 95% confidence interval (CI), we can plot the number in each cluster against the estimated power.

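### The Objective 2 sample size of 140 is checked against infants enrolled, but the Bland-Altman analysis needs infants with both a TcB and an SBR, and the protocol does not secure that number of pairs

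*Protocol*

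**What the plan says.** Protocol section 10.1, Primary Objective 2, derives a Bland-Altman sample size. On the effect size it says "we take a mean difference of 10 to be our estimated effect size". It takes the SD of the differences as 57.4 and the agreement limit as 145 µmol/L. It concludes that the objective "requires 140 study participants , which from above we should easily exceed".

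The figure it points back to is the Objective 1 enrolment. Section 8 says "it has been estimated that a total of 560 participants will need to be recruited", which is 28 per hospital with 20 hospitals ("We assume that we will have 20 hospitals collecting data", section 10.1, Primary Objective 1).

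On who has which test:
- Section 7.1 admits an infant at the first objective bilirubin assessment, whatever the reason. Under Screening and recruitment in section 9, ward staff are to "alert the research team when any neonates are undergoing their first TCB or SBR".
- Laboratory assessments in section 9: "SBR measurements will only be done by the normal clinical team as part of routine clinical care".
- Section 7 says "TcB is commonly used in neonates over 24 hours of age" and describes SBR as following TcB readings that lie within some threshold of the phototherapy line.

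Section 10.2 plans the Objective 2 analysis "stratified by method of how the measurement for how serum bilirubin was taken". It also plans to redo the sample sizes on accumulating data until both primary objectives have reached theirs. The footnote to Table 1 lists three SBR types: blood gas, laboratory and spun.

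**The concern.** A TcB-SBR difference exists only for an infant who has both measurements. The protocol counts every enrolled infant towards the 140, although a single test is enough for enrolment and the study adds no SBR. On the protocol's own description of care, some infants will have a TcB with no SBR, and some may have an SBR with no TcB. The number of analysable pairs is then smaller than 560 by an amount the protocol neither states nor assumes.

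At stake is whether a primary objective is adequately sized. While the target is worded in participants, 560 enrolled infants look like four times the requirement whatever the number of pairs.

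**Working it through.** **Inputs from the protocol.** Enrolment 28 × 20 = 560 (sections 8 and 10.1). Mean difference 10, SD √(43² + 38²) = 57.385 (printed as 57.4), agreement limit 145 and stated N 140 (section 10.1, Primary Objective 2). The 80% there is printed as a sample size; I read it as power.

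**Assumptions.** Alpha is not stated for Objective 2; I take 0.05 two-sided with 95% limits of agreement. The pair fraction is not in the documents, so I vary it.

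**Step 1: the protocol's own figure.** For n pairs, the standard error of a limit of agreement is

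SE = SD × √(1/n + 1.96² / (2(n − 1))).

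The non-centrality for the nearer limit is (145 − 10 − 1.96 × SD)/SE and for the farther one (145 + 10 − 1.96 × SD)/SE. Power is 1 minus the sum of the two type II errors, from the non-central t distribution on n − 1 degrees of freedom.

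At n = 140 with SD 57.4:
- SE = 57.4 × √(1/140 + 3.84/278) = 8.31
- nearer limit: (135 − 112.5)/8.31 = 2.71, type II error 0.233
- farther limit: (155 − 112.5)/8.31 = 5.11, type II error 0.001
- power = 1 − 0.233 − 0.001 = 0.766

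Power first reaches 0.80 at n = 152 (0.797 at 151, 0.800 at 152). Normal instead of t, or a 3·SD²/n variance, gives 150 to 156. The printed 140 is therefore not reproduced from the printed inputs; cutting the SD to 57 gives 141.

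**Step 2: break-even pair fraction.** 140/560 = 25% of all enrolled infants. For 152 it is 152/560 = 27%.

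**Step 3: pairs and power over a range of assumed fractions** (unrounded SD; using 57.4 lowers power by at most 0.2 percentage points).

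| Enrolled infants with both tests (assumed) | Pairs from 560 | Power, pooled sample |
|---|---|---|
| 15% | 84 | 52% |
| 20% | 112 | 67% |
| 25% | 140 | 77% |
| 30% | 168 | 84% |

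**Step 4: what the re-estimation would see.** Section 10.2 limits the interim data to bilirubin measures, skin tone and age at TcB. Pairs could be counted from these, but nothing says they will be, and the Objective 2 target carried forward is in participants. SBR type, which defines the strata of the analysis, is not among the interim data.

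**The case against.** The strongest reply is the re-estimation in section 10.2. It continues until both primary objectives have their numbers and may lengthen the study. The synopsis calls 560 a minimum, and section 8 lets recruitment windows reopen for under-recruited skin tone groups. This stands as a partial safeguard. A reader might infer that recruitment will simply stop at 560 with Objective 2 short; the documents do not support that. What remains is that the rule runs on a target in the wrong unit.

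Three other stronger readings also fail.
- **Only infants over 24 hours have a TcB.** One could take the simulation's uniform 0 to 96 hours, keep 75% of 560 = 420, and require 140/420 = 33% of these to have an SBR. But section 7 says TcB is common after 24 hours, not confined to it, and notes that local guidelines vary. The age range is a device of the power simulation, not a forecast. The same simulation puts mean bilirubin 80 to 140 µmol/L above the line it gives for phototherapy, which would send nearly every infant to SBR.
- **140 is needed in each SBR method or skin tone.** The protocol sets one total. Three SBR types by four tones is 12 cells, but no requirement is stated for a cell and no split between types is given.
- **The stratified analysis should give way to a single model.** A model with a common tone effect would not, as such, yield tone-specific limits of agreement. Section 5.1 reports that an earlier study found greater variance in darker tones. The stratified analysis can stay.

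**Conclusion.** The point holds as a unit error in the sample size of a primary objective. The protocol compares a requirement for pairs with a count of enrolled infants and gives no fraction to connect them, so its assurance has no basis in the document.

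It does not follow that 140 pairs will be missed. Any pair fraction above 25% reaches 140 in the pooled sample, and nothing in the documents places the true fraction on either side of that. Across assumed fractions of 15% to 30%, pooled power runs from about 52% to 84%. Those figures rest on the protocol's mean difference, SD and agreement limit, taken as given, and on the assumed two-sided alpha of 0.05. The gap between 140 and 152 is a secondary matter; it affects the fix because restating 140 in pairs would not by itself deliver 80% power on the printed inputs.

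**What to change.** In section 10.1, Primary Objective 2:
- State the target as infants with a TcB-SBR pair, and delete the clause saying that enrolment will comfortably cover it.
- State the assumed pair fraction with a range, noting that 25% of those enrolled is break-even for 140.
- Recheck the 140 or restate its power: the printed inputs give about 77% at 140 and 80% at 152, with alpha 0.05 two-sided. State the alpha used.
- Say that the target is for the pooled sample, so results by SBR method and by skin tone will be less precise.

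In section 10.2:
- State that each re-estimation counts pairs, overall and by skin tone and SBR type, and add SBR type to the interim data.
- State that recruitment for Objective 2 is judged on pairs.

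Keep the stratified analysis. The cost is a few sentences, one extra count at re-estimations already planned from data already collected, and possibly a less favourable stated figure.
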